4.1.2 Secondary and Exploratory Efficacy Variables

The secondary and exploratory efficacy variables are the following:

- Clinical Global Impression of Improvement (CGI-I) score (secondary)
- Triple Timed Up and Go (3TUG) result (exploratory)
- Subject most bothersome symptom question (exploratory)
- QMG limb domains (exploratory)

The calculations and analyses pertaining to each of the above variables are shown in Section 4.2.2.

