4.2.2 Secondary and Exploratory Efficacy Analyses

Secondary and exploratory efficacy analyses will be conducted on the FAS and PP populations, with the FAS population serving as the primary analysis set.

Clinical Global Impression of Improvement (CGI-I)

CGI-I scores will be summarized by treatment group using descriptive statistics. A Wilcoxon Rank Sum Test will be conducted to assess for treatment group differences.

Triple Timed Up and Go (3TUG)

The number and proportion of subjects with at least a 20% increase in average time for 3TUG (i.e., a success) at Day 4 relative to Day 0 will be presented by treatment. For those subjects that are unable to complete the Day 4 assessment due to disability related to their disease, a success will be assigned to the subject by the site at the time of testing. The proportion will be computed in two ways: 1) using all subjects in the analysis population with Day 0 data as the denominator, regardless of whether or not they completed the Day 4 assessment; and 2) using only those subjects in the analysis population who completed both the Day 0 and Day 4 assessments. For each approach in calculating the proportion, a two-sided Fisher's Exact Test will be conducted to

test for a significant difference in the success proportions between treatment groups.

Patient Most Bothersome Symptom Question

For the Patient Most Bothersome Symptom (PMBS) question, change from baseline (CFB) will be computed as the post-treatment response (Day 4) minus the Baseline response (Day 0). The post-treatment response will be the result obtained on Day 4, unless the subject discontinued treatment early, in which case the post-treatment response may be obtained at an earlier time point.

Summary statistics for the PMBS Day 0 response, PBMS Day 4 response, and the corresponding CFB will be presented by treatment. The analysis of CFB for PMBS Score will be performed using Wilcoxon's Rank Sum Test.

QMG Limb Domains

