^a P-value based on the Wilcoxon Rank Sum Test for treatment differences. Table Creation Date: (DD-MMM-YYYY) Source Program: xxxxxx.sas Source Listing: Data Listing 15

Treatment	Dose Group	Time Point	Data Type	Mean	Std Dev	n	Min	Max	Median
Amifampridine	Dose Group	IIME IOINC	Data Type	Mean	Dev	11	PILII	Max	Meditan
mariampridine	Loui Doco (< 60mg/dour)	Davi 4	RAW						
	Low Dose (< 60mg/day)	Day 4		XXX	XXX	XXX	XXX	XXX	XXX
	High Dose (> 60mg/day)	Day 4	RAW	XXX	XXX	XXX	XXX	XXX	XXX
	All Doses	Day 4	RAW	XXX	XXX	XXX	XXX	XXX	XXX
Placebo		-							
	Low Dose (< 60mg/day)	Day 4	RAW	XXX	XXX	XXX	XXX	XXX	XXX
	High Dose (> 60mg/day)	Day 4	RAW	XXX	XXX	XXX	XXX	XXX	XXX
	All Doses	Day 4	RAW	XXX	XXX	XXX	XXX	XXX	XXX

Table 27. CGI-I Scores Summary Statistics by Dose Group Catalyst Pharmaceuticals, Inc. - LMS-003 FAS Population (N=xxx)

Table Creation Date: (DD-MMM-YYYY) Source Program: xxxxxx.sas Source Listing: Data Listing 15

Table 29. Number and Proportion of Subjects with ≥ 20% Increase in 3TUG Average Time Catalyst Pharmaceuticals, Inc. - LMS-003 FAS Population (N=xxx)

Calculation	Amifampridine (N=xxx)	Placebo (N=xxx)	P-value ^a
Denominator Based on Subjects Who Completed Day 0 3TUG	xxx/xxx (xxx)	xxx/xxx (xxx)	XXX
Denominator Based on Subjects Who Completed Day 0 and Day 4 $3 extsf{TUG}$	xxx/xxx (xxx)	xxx/xxx (xxx)	XXX

^a P-value based on a two-sided Fisher's Exact Test of difference in treatment proportions. Table Creation Date: (DD-MMM-YYYY) Source Program: xxxxxx.sas Source Listing: Data Listing 16

Table format will be repeated for the PP Population.

STATKING Clinical Services Version 1.0

Page 38 of 71

Table 31. Number and Proportion of Subjects with \geq 20% Increase in 3TUG Average Time by Dose Group Catalyst Pharmaceuticals, Inc. - LMS-003 FAS Population (N=xxx)

Low Dose(< 60mg/day)

High Dose(\geq 60mg/day)

Calculation	Amifampridine (N=xxx)	Placebo (N=xxx)	Amifampridine (N=xxx)	Placebo (N=xxx)
Denominator Based on Subjects Who Completed Day 0 3TUG	xxx (xxx%)	xxx (xxx%)	xxx (xxx%)	xxx (xxx%)
Denominator Based on Subjects Who Completed Day 0 and Day 4 3TUG	xxx (xxx%)	xxx (xxx%)	xxx (xxx%)	xxx (xxx%)

Table Creation Date: (DD-MMM-YYYY) Source Program: xxxxxx.sas Source Listing: Data Listing 16

Table 33. Summary of Patient Most Bothersome Symptom Catalyst Pharmaceuticals, Inc. - LMS-003 FAS Population (N=xxx)

Treatment	Time Point ^a	Data Type ^b	Mean	Std Dev	n	Min	Max	Median	P-value ^c

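### The second 3TUG test removes the patients the SAP has just counted as worsened, so it selects on a post-randomization outcome and can shift the result either way

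*SAP*

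**What the plan says.** SAP 4.2.2 defines the 3TUG event by counting "subjects with at least a 20% increase in average time for 3TUG (i.e., a success) at Day 4 relative to Day 0". The SAP's label for this event is favourable, but the event is a worsening. The next sentence deals with patients who cannot do the test, in these words: "unable to complete the Day 4 assessment due to disability related to their disease, a success will be assigned to the subject". The site makes that assignment during the test visit.

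The proportion is then calculated in two ways:

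- **Method 1** (wider denominator): "using all subjects in the analysis population with Day 0 data as the denominator, regardless of whether or not they completed the Day 4 assessment".
- **Method 2** (narrower denominator): "using only those subjects in the analysis population who completed both the Day 0 and Day 4 assessments".

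Each method gets its own two-sided Fisher's exact test. The Table 29 shell in SAP Appendix B gives each a row with a p-value. The first row is labelled "Denominator Based on Subjects Who Completed Day 0 3TUG"; the second requires completion on both days. The SAP does not say which is the main analysis or whether either is a sensitivity analysis. Protocol 13.4 plans one Fisher test and does not mention two denominators. SAP 4.1.2 lists 3TUG as exploratory.

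**The concern.** The SAP describes the patients with an assigned event as unable to complete the Day 4 assessment. Method 2 admits only patients who completed it. Read plainly, method 2 undoes the rule stated just before it and discards the worst outcomes on this measure.

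Inability on Day 4 can arise only after randomization. Protocol 8.2.1 requires patients to be able to perform all assessments at entry, and 8.2.2 excludes those who cannot ambulate. Method 2 therefore compares groups that are no longer as randomized whenever treatment affects inability.

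Method 1 has a smaller fault in the other direction. A patient with a Day 0 time and no Day 4 test for a reason other than disability stays in the denominator and counts as not worsened, although SAP 2.3 says that no values are imputed.

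With two equally ranked p-values for one endpoint, the tests can fall on opposite sides of 0.05, and the choice of which to report first is left until the results are known.

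**Working it through.** The documents give no 3TUG power or event rate, so there is no planned figure to reproduce.

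**Inputs from the documents.** 26 patients, 13 per arm (SAP 1.3); two-sided Fisher test at 0.05 (SAP 2.1 and 4.2.2). In LMS-002 the LS mean QMG score rose by 2.2 on placebo and 0.4 on amifampridine (Protocol 6.4.2), which bears on where disability is likely to fall.

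**Assumed inputs.** Let *q* be the probability of being unable to do the Day 4 test and *s* the probability of slowing by at least 20% among those tested. Subscripts are A for amifampridine and P for placebo. If the percentage change is normal with SD 20, a mean of 0 on amifampridine gives *s*A = 1 − Φ(1) = 15.9%, taken as 16%. A mean of +20 on placebo gives *s*P = 50%.

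**What each method compares.** Method 1 compares *q* + (1 − *q*)*s* between arms. Method 2 compares *s* alone. Placebo minus amifampridine therefore changes by

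method 1 − method 2 = *q*P(1 − *s*P) − *q*A(1 − *s*A).

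Method 2 shrinks the difference only if *q*P(1 − *s*P) > *q*A(1 − *s*A). With the rates above this is 0.50*q*P > 0.84*q*A, so placebo inability must exceed 0.84/0.50 = 1.68 times that on amifampridine. Below that ratio method 2 enlarges the difference.

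**Power by exact enumeration, 13 per arm, *s* = 16% v 50%.**

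| Unable, A / P | Difference, method 1 | Difference, method 2 | Power, method 1 | Power, method 2 |
|---|---|---|---|---|
| 0% / 5% | 52.5 − 16.0 = 36.5 points | 34.0 | 39% | 36% |
| 0% / 15% | 57.5 − 16.0 = 41.5 points | 34.0 | 50% | 35% |
| 15% / 15% | 57.5 − 28.6 = 28.9 points | 34.0 | 24% | 29% |

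The 57.5 is 15 + 0.85 × 50, and the 28.6 is 15 + 0.85 × 16. With *s*A left unrounded at 15.9%, the last cell is 30%.

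**A second set of assumptions (*s* = 10% v 50%)** gives the same pattern. With inability on placebo only, power for method 1 v method 2 is 60% v 52% at 10% unable, 71% v 49% at 20% and 80% v 47% at 30%. With 10% unable in both arms it reverses, to 37% v 47%.

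**Single-table examples (events/patients, amifampridine v placebo).**

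- Method 1: 1/13 v 8/13, p = 0.011. If 2 of the 8 placebo events are patients unable to do the test, method 2 has 1/13 v 6/11, p = 0.023. If 3 are, it has 1/13 v 5/10, p = 0.052.
- Method 1: 2/13 v 8/13, p = 0.041. With 2 placebo patients unable, method 2 has 2/13 v 6/11, p = 0.083. With 2 unable in each arm, it has 0/11 v 6/11, p = 0.012.

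The two tests can thus disagree at 0.05, and method 2 can give the larger or the smaller p-value.

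**The case against.** A reader might infer that method 2 is inherently biased toward no effect. The documents do not support that. The direction depends on how inability divides between the arms, and no inability rate is given. What they do support is plausibility: amifampridine patients continue a stable dose, placebo patients are withdrawn from it, and placebo patients worsened more in LMS-002.

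Inability may also be uncommon. Protocol Appendix 4 allows a usual cane or walker and standing rests. Protocol 11.4 asks patients who discontinue early to do the 3TUG, and SAP 2.3 analyses rescue-time observations with the Day 4 data. Rescued patients who can still do the test therefore remain in method 2. This limits the size. It does not help patients who cannot perform the test, because they have no measured time.

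Method 1 is prespecified, listed first and keeps assigned events in both numerator and denominator. Both rows appear in one table, so a disagreement would be visible, and a completers analysis shown alongside is ordinary practice. All of this stands. What remains is that the SAP does not call method 2 supportive and gives it an equal p-value.

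The fault in method 1 is narrow. The FAS already requires a post-treatment efficacy assessment, so it affects only a patient with some other post-treatment result but no 3TUG, for a reason unrelated to disability.

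**Conclusion.** The point holds. Method 2 excludes the patients to whom the SAP has just assigned the event, so it selects on a post-randomization outcome, and it ranks equally with a test that does not drop them. It attenuates the difference if inability is concentrated on placebo and can exaggerate it if inability is similar in the two arms.

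The size is illustrative and rests wholly on assumed rates. With inability on placebo only, the loss of power runs from 3 percentage points at 5% unable (39% v 36%) to 15 points at 15% unable (50% v 35%). With 15% unable in both arms, method 2 gains about 5 points.

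Severity is minor. The endpoint is exploratory and unpowered, it plays no part in the co-primary decision, and method 1 keeps the disabled patients. A reader might go further and take the 3TUG result as unusable or the trial's conclusion as at risk; nothing in the documents supports either.

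**What to change.** In SAP 4.2.2, name one main 3TUG analysis in the FAS. The Day 4 (or early-discontinuation) outcome is either a measured time or the assigned disability event, and assigned events count in both numerator and denominator.

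Then do one of the following with method 2:

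- relabel it as a supportive completers analysis; or
- change it to exclude only tests missing for reasons other than disability.

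Report the number of such missing tests by arm, because method 1 counts them as not worsened. Change the Table 29 row to match.

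This is a cheap improvement. The cost is one extra SAP sentence and a changed table row; no data collection changes.

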5.0 Analysis of Safety

The safety variables for this study are:

- Adverse events (AE)
- Vital signs (screening, Days 1-4)

- Physical examination (at screening only)
- Concomitant medications

Adverse Events

All AEs will be observed for each subject from enrollment until termination from the study. Prior to analysis, all AEs will be coded using MedDRA. Based on these coded terms, treatment emergent AEs (TEAEs) will be summarized using system organ class and preferred term by treatment and overall for all subjects in the safety population. This analysis will be repeated for serious TEAEs (TESAEs).

TEAEs will also be summarized by severity and relationship to IP. An overall summary table will provide the highest relationship and maximum severity observed per subject, as well as the counts of subjects with at least one TESAE.

All AEs will be listed, regardless of whether or not they were treatment emergent. AEs having an end date prior to signing the informed consent for this study will not be displayed in the AE data listings.

Vital Signs

Summary statistics (mean, median, sample size, standard deviation, minimum, and maximum) will be computed on the raw and change from baseline values for each vital sign parameter by time point, for each treatment. The screening time point will serve as baseline. If there are multiple vital signs taken at any time point, then the latest set of vital signs will be used for the analysis. All vital sign data will be listed.

Physical Exam

The physical exam data collected at screening will be listed.

Concomitant Medications

A table of the WHO-coded medications will be constructed by treatment group and overall with medications summarized by level 3 anatomical therapeutic chemical (ATC) term and Preferred Term. The number and percent of subjects on each drug will be summarized. A data listing for all concomitant medications will be provided.

6.0 Other Relevant Data Analyses/Summaries

6.1 Subject Completion

A table will be constructed with counts of screen failures and enrolled subjects. Of those enrolled, counts and percentages of the number of subjects withdrawing from the study before study completion and the number completing the study will be displayed. For those subjects that withdraw before completion of the study, counts and percentages of the reasons for withdrawal will be tabulated. The table will include summary counts and percentages by treatment. A data listing of all subject completion and withdrawal data will also be constructed.

6.2 Study Drug Administration and Compliance

Duration of treatment administration will be computed per subject as:

Duration (in days) = (Date of last dose) – (Date of first dose) + 1

Duration will be summarized using descriptive statistics by treatment group.

Compliance will be computed per subject as:

Compliance = 100%*(Number consumed)/(Number prescribed),

where number prescribed is defined as the duration times the number of tablets to have been taken daily. Compliance will be summarized using descriptive statistics by treatment group.

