8.3.3 Directions for Administration

The dose of amifampridine phosphate will be individually determined by the Investigator, within the bounds of a total daily dose of 30 mg to 80 mg, divided into doses taken 3 to 4 times per day as prescribed by the Investigator, based on optimal neuromuscular benefit.

All doses of study medication will be taken orally by mouth.

Generally, doses of study treatment will be taken outside the clinic, except during the in-clinic study visit. If the patient takes the dose three or four times a day, the patient should be given specific instructions on dosing relative to the time of their visit to assure a dose will be given during the in-clinic visit, corresponding to the second, third, or fourth dose. A **dose must be administered in the clinic in order to perform efficacy assessments at the correct time in relation to dosing.** Safety assessments are to be performed **before the dose** administered to the patient during the scheduled in-clinic visit. All efficacy assessments will be performed at times relative to the dose administered in the clinic. **In this case, the dose will be 40 minutes before the first efficacy assessment.**

Page 36

Assessment	Start Time After Dose* (+ 10 minutes unless otherwise specified)
SGI	40 minutes
Patient most bothersome symptom	Following SGI
QMG	Following patient symptom evaluation
CGI-I°	Following QMG
3TUG	Following CGI-I

^{*}Administration of medication represents Time 0 (minutes)

If the patient is taking pyridostigmine, the dosing schedule must be fixed in relation to when they take the IP, such that on the days of clinic assessments the timing between pyridostigmine dose and IP do not vary.

Assessments for each clinic visit must be performed relative to the same dose as occurred on Day 0.

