11.2 Randomization Visit (Study Day 0)

The study activities listed below will be performed on Study Day 0, while the patient has been on open-label amifampridine phosphate and in relationship to the usual dosing schedule.

Assessment	Start Time After Dose* (+ 10 minutes unless otherwise specified)
SGI	40 minutes
Patient most bothersome symptom, Question 1	Following SGI
QMG	Following patient symptom evaluation
3TUG	Following QMG

^{*}Administration of medication represents Time 0 (minutes)

- Assessment of AEs/SAEs
- Assessment of concomitant medications

Patients who are deemed eligible will be dispensed double-blind study medication (amifampridine phosphate or placebo tablets) on Study Day 0, according to the treatment group to which they are randomized. The patient's open-label amifampridine must be collected. Patients must stop their open-label amifampridine and will start to take the blinded study

Page 50

medication beginning with the next scheduled dose after all assessments on open-label medication have been completed.

Patients must be instructed that they are not to take any doses of their prior, open-label amifampridine during the study and not to change pyridostigmine dose or schedule.

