11.3 End of Treatment (Study Day 4)

Patients will take their blinded study medication on Days 1-3. On Day 4, a dose of blinded study medication must be administered by the site study personnel. This is the same medication that the patient has been taking on Days 1-3. The assessments listed below will be performed **following either the second, third, or fourth dose of medication to be taken on Day 4, and this should be the same dose that assessments on Day 0 were subsequently performed.** For example, if the patient took their second dose of amifampridine in the clinic on Day 0 and had assessments started 40 minutes later, then on Day 4, that patient should be assessed after taking their second dose of medication in the clinic, starting 40 minutes after the dose.

Safety assessments (vital signs and AEs/SAEs) should be performed before study personnel give the dose of blinded medication. Concomitant medications should be reviewed for any changes. A urine sample, to determine amifampridine level, should be collected on Day 3 (after patient has taken a dose of blinded medication), and on Day 4, before study personnel give the dose of blinded medication.

Assessment	Start Time After Dose* (+ 10 minutes unless otherwise specified)
SGI	40 minutes
Patient most bothersome symptom, Question 2	Following SGI
QMG	Following patient symptom evaluation
CGI-I (compared to Day 0)	Following QMG
3TUG	Following CGI-I

^{*}Administration of medication represents Time 0 (minutes)

Page 51

The container of blinded study medication dispensed on Study Day 0 must be returned to study personnel and the IP Accountability form completed to determine if the blinded study medication doses were taken.

This represents the end of the study.

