1.1 Design and Treatment

Subjects will be randomized on Day 0 to either treatment group in a 1:1 ratio. Investigational product (IP) will be administered under double-blind conditions such that neither the Investigator nor subject knows if they are taking placebo or amifampridine phosphate.

Amifampridine phosphate (at the subject's optimal dose established prior to enrollment into this trial) or placebo will be dispensed by the site pharmacist, according to the randomization schedule, to begin with the next dose after all Day 0 assessments are completed and continued for 4 days. Although subjects at the high (dose \geq 60 mg/day) and low (dose < 60 mg/day) are randomized separately, the study is not powered to detect differences across dose levels and no inferential analyses are planned to compare dose levels (See Section 1.3). The amifampridine phosphate dose is 30 mg to 80 mg total daily dose (expressed as freebase form), given in 3 to 4 divided doses, with no single dose >20 mg.

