1.2 Study Procedures

The planned duration of participation for each subject is 5 days (Day 0 through Day 4), excluding the screening period, which can last up to 7 days. Those subjects satisfying all inclusion and exclusion criteria will be randomized to a Treatment Group on the last day of the screening period (Day 0). The treatment period will take place on the remainder of Day 0 and Days 1 through 4. The following assessments will be performed at the beginning and end of the 4-day treatment period:

- Vital signs
- Urine sample for amifampridine level (collected at days 3, and 4)
- Clinical Global Impression of Improvement (CGI-I)
- Subject Global Impression (SGI)
- Quantitative Myasthenia Gravis (QMG)
- Triple Timed Up and Go (3TUG)
- Patient most bothersome symptom question
- Record concomitant medications
- Monitor for adverse events (throughout the 5-day treatment period)

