2.2 Analysis Populations

The following analysis populations will be defined:

Safety: This population consists of all randomized subjects who receive at least 1 dose of IP (amifampridine or placebo).

Full Analysis Set (FAS), Intent to Treat Population: This population consists of all randomized subjects who receive at least 1 dose of IP (amifampridine or placebo) and have at least one post-treatment efficacy assessment.

Per Protocol (PP): This population is a subset of the FAS population, excluding subjects with major protocol deviations. The PP population will include all subjects who:

- Have no major protocol deviations or inclusion/exclusion criteria deviations that might potentially affect efficacy, and
- Subjects who took at least 80% of the required treatment doses and remained enrolled for at least 4 days.

Evaluations obtained at the time of discontinuation will be included in the FAS and PP analyses, as applicable. Subjects who discontinue with no post-randomization data (no Day 0 and no Day 4 data) will be excluded from all efficacy analyses but will be included in the safety analyses.

Exclusion from the FAS and PP Populations will be finalized prior to database lock and subsequent unblinding.

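### The compliance formula counts the part days 0 and 4 as two full days, so a fully adherent patient scores 80.0% at a Day 4 visit unless the clinic dose is the last of the day

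*SAP*

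**What the plan says.** SAP 6.2 takes duration as the date of last dose minus the date of first dose, plus 1. Compliance is 100% times number consumed over number prescribed, "where number prescribed is defined as the duration times the number of tablets to have been taken daily". The footnote to Data Listing 11 repeats that definition. Neither place adjusts for part days.

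The start and end of blinded dosing are fixed elsewhere:

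- **Start.** Protocol 11.2 has patients take blinded drug "beginning with the next scheduled dose after all assessments on open-label medication have been completed". SAP 1.2 says: "The treatment period will take place on the remainder of Day 0 and Days 1 through 4".
- **Clinic dose.** Protocol 8.3.3 requires a dose in the clinic, "corresponding to the second, third, or fourth dose". For Day 4, Protocol 11.3 adds that "this should be the same dose that assessments on Day 0 were subsequently performed".
- **End.** Protocol 11.3 says of the Day 4 visit: "The container of blinded study medication dispensed on Study Day 0 must be returned to study personnel". It also makes that visit the end of the study.
- **Intended length.** SAP 1.1 has dosing "to begin with the next dose after all Day 0 assessments are completed and continued for 4 days".

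The per-protocol (PP) set in SAP 2.2 admits "Subjects who took at least 80% of the required treatment doses and remained enrolled for at least 4 days".

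**The concern.** Patients take blinded drug on only part of Day 0 and only part of Day 4. Because the clinic dose has the same number on both days, the doses after it on Day 0 and the doses up to and including it on Day 4 make up exactly one day's tablets. The formula charges two. Over months of dosing one extra day would not matter. Here it raises the denominator from 4 days to 5, which is 25%.

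The error also varies between patients. If the clinic dose is the last of the day, no blinded dose falls on Day 0 and the formula is right. Two patients who each took every tablet can then score 80% and 100% because of clinic-dose timing alone.

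The compliance summary in Table 4 and the listing behind it are directly at stake. Membership of the PP set is at stake conditionally. The artefact lands exactly on the 80% threshold, the SAP offers no other adherence formula, and both co-primary endpoints are repeated on that set (Tables 14 and 22) in a trial of about 28 patients.

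**Working it through.** The documents give no expected compliance value to reproduce, only the formula, so the check is a direct count.

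**Inputs.** Doses per day n = 3 or 4, and clinic dose number k = 2, 3 or 4, the same on Day 0 and at the final visit (Protocol 8.3.3 and 11.3). Final visit on day L = 4, or L = 5 under the +1 day window (Protocol 8.1). The permitted pairs (n, k) are (3,2), (3,3), (4,2), (4,3) and (4,4).

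**Full adherence, clinic dose not last of the day (k < n).**

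- Doses taken: (n − k) on Day 0, n on each of Days 1 to L − 1, and k on day L. The total is (n − k) + (L − 1)n + k = L × n.
- Duration = L + 1, so prescribed = (L + 1) × n.
- Score = L/(L + 1): 4/5 = 80.0% for L = 4 and 5/6 = 83.3% for L = 5.

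Unequal doses within the day do not change this, because the two part days still sum to one day's tablets. Example: 60 mg/day as three doses of two 10 mg tablets, k = 2, L = 4. Tablets taken are 2 + 18 + 4 = 24, prescribed 5 × 6 = 30, and 24/30 = 80.0%.

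**Full adherence, clinic dose last of the day (k = n).** The first blinded dose is on Day 1, duration is L, and the score is 100%.

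Three of the five permitted pairs are therefore affected: (3,2), (4,2) and (4,3).

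**Reversed ranking.** A patient on an affected schedule who skips every Day 0 blinded dose has duration 4 instead of 5. With equal doses and a Day 4 visit the scores are 11/12 = 91.7% for (3,2), 14/16 = 87.5% for (4,2) and 15/16 = 93.8% for (4,3). All exceed the 80.0% given to a patient who missed nothing.

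**One missed dose, if 6.2 is used for the PP rule.** Equal doses are assumed. The in-clinic dose is left out because study personnel give it.

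| (n, k) | Day 4: below 80% | Score | True | Day 5: below 80% | Score | True |
|---|---|---|---|---|---|---|
| (3,2) | 10 of 11 | 11/15 = 73.3% | 11/12 = 91.7% | 13 of 14 | 14/18 = 77.8% | 14/15 = 93.3% |
| (4,2) | 15 of 15 | 15/20 = 75.0% | 15/16 = 93.8% | 19 of 19 | 19/24 = 79.2% | 19/20 = 95.0% |
| (4,3) | 14 of 15 | 15/20 = 75.0% | 15/16 = 93.8% | 18 of 19 | 19/24 = 79.2% | 19/20 = 95.0% |
| Total | 39 of 41 | | | 50 of 52 | | |

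The two exceptions in each total are the sole Day 0 dose in (3,2) and (4,3). Missing it shortens the duration, so the patient passes. Some unequal splits also pass at Day 5: with 20/20/10 mg, k = 2 and one 10 mg dose missed, 24/30 = 80.0%. When the clinic dose is the last of the day, no single missed dose falls below 80%.

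**Early stopping.** If a patient on an affected schedule takes every dose and stops at the same-numbered dose on Day 3 or Day 2, the score is 3/4 = 75.0% or 2/3 = 66.7%. Other stopping points give other values.

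**The case against.** The arithmetic is hard to dispute. The case on the other side concerns consequence.

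- **The PP rule speaks of required doses and does not cite 6.2.** On its ordinary meaning, one missed dose is 11/12 or 15/16 of what was required, and the patient stays in. This stands: the PP effect is conditional. Even under the adverse reading, a patient who completes to Day 4 or Day 5 and misses nothing meets the threshold.
- **Adherence has other sources.** Protocol 8.3.7 relies on reconciling used and unused product and on urine specimens, and PP exclusions are settled before database lock and unblinding, so an odd score could be noticed. But 8.3.7 gives no percentage, and the possibility of noticing an artefact does not correct the formula.
- **Five calendar days is a defensible exposure duration.** The adverse-event item in SAP 1.2 does refer to a five-day treatment period. That supports the duration figure but not multiplying it by a full day's tablets.
- **Patients might finish their Day 4 doses at home.** Returning the container points the other way. Even so, with equal doses, full adherence would score 17/20 = 85.0% for (4,3), 13/15 = 86.7% for (3,2) and 18/20 = 90.0% for (4,2).
- **The counts are of schedules and dose positions, not patients.** This stands. The documents do not give the mix of schedules, so the affected share of patients is unknown.
- **The early-stop scores are unlikely to decide PP status.** This also stands, since such patients appear to fail the four-day enrolment condition anyway.
- **Table 4 is descriptive and the formula is the same in both arms.** True, and it limits the weight of the point.

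**Conclusion.** The concern holds. Applied as written, SAP 6.2 gives full adherence a score of 80.0% at a Day 4 visit and 83.3% at a Day 5 visit in three of the five permitted combinations of doses per day and clinic dose. It gives 100% in the other two. It can also rank a patient who skipped the Day 0 doses above one who took everything.

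This rests on blinded dosing ending with the in-clinic dose at the final visit, as Protocol 11.3 implies, and on the clinic dose having the same number on both days.

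The misreporting in Table 4 and Data Listing 11 is certain for any patient on an affected schedule. The PP consequence arises only if 6.2 is used to apply the 80% rule. The FAS analysis of the co-primary endpoints, which is primary, does not change. The plan should be corrected, but its main conclusion does not depend on this.

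**What to change.** In SAP 6.2, define number prescribed as the tablets scheduled from the first scheduled blinded dose after the Day 0 assessments, whether that falls on Day 0 or Day 1, through the in-clinic dose at the final visit. For a completer this is 4 × daily tablets at a Day 4 visit and 5 × daily tablets at a Day 5 visit, so dose times are not needed. Starting from the first scheduled dose, not the first dose taken, also removes the reversed ranking. For early discontinuation, use the tablets scheduled up to the last dose; Protocol 11.4 already has its date and time recorded. Calendar-day duration can stay as the exposure measure.

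State that SAP 6.2, Table 4, Data Listing 11 and the PP 80% rule all use this denominator. Full adherence then scores 100% on every schedule, and one missed dose with equal doses and a Day 4 visit scores 91.7% (three doses a day) or 93.8% (four).

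The cost is one definition (with the matching Data Listing 11 footnote), one cross-reference in SAP 2.2 and one line of programming. It should be settled before PP exclusions are finalised.
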